5. SUBJECT ENROLLMENT

Before subjects may be entered into the study, Amgen requires a copy of the site's written independent ethics committee and/or institutional review board (IEC/IRB) approval of the protocol, informed consent form (ICF), and all other subject information and/or recruitment material, if applicable (see [Section 11.2](#)). All subjects must personally sign and date the informed consent form before commencement of study specific procedures. A subject is considered enrolled once they have signed the informed consent form for this study.

All subjects that have not participated in an AMG 145 parent protocol who enter this study will be assigned a unique subject identification number. All subjects who enter the study after finishing a parent study will be assigned the same unique subject identification number from the parent study, except subjects that participated in phase 1 studies.

6. TREATMENT PROCEDURES

AMG 145 will be the investigational product in this study.

An Investigational Product Instruction Manual (IPIM) containing detailed information regarding the storage, preparation, and administration of the investigational product will be provided separately.

6.1 AMG 145

Investigational product will be administered by SC injections in this study. AMG 145 in its original formulation is currently used in this study, which requires larger total volumes of administration and use of vials and syringes. A new (more concentrated) formulation of AMG 145 has recently become available, which reduces the volume of a 420 mg injection and allows for administration by 3 prefilled autoinjector/pen devices or one personal injector device. As reduced injection volume and the added convenience of using a device to administer the injection will benefit study subjects, the new formulation and prefilled autoinjector/pen device or personal injector will be introduced to study subjects when they are available for dispensation to sites

Initial Formulation:

AMG 145 will be manufactured and packaged by Amgen Inc. and distributed using Amgen clinical IP distribution procedures. AMG 145 will be presented as a sterile, clear, colorless frozen liquid. Each sterile vial is filled with a 1-mL deliverable volume of 70 mg/mL AMG 145 formulated with [C] mM sodium acetate, [C]% (w/v) sucrose, [CC] % (w/v) polysorbate 20, pH [CC]. Each vial is for single use only.

AMG 145 should be stored protected from light and according to the storage and expiration information (where required) provided on the label. AMG 145 should be thawed per the instructions provided in the IPIM. Vials should be checked for cracks or damage that may occur if the thawing process is not performed properly. Damaged product should not be administered. Further details are provided in the IPIM.

New Formulation:

AMG 145 will be manufactured and packaged by Amgen Inc. and distributed using Amgen clinical IP distribution procedures. When available in each country, AMG 145 will be presented as a sterile, preservative-free solution in a single use, disposable, handheld mechanical (spring-based) prefilled autoinjector/pen (AI/Pen) for fixed dose, subcutaneous injection. The prefilled AI/Pen contains a 1-mL deliverable volume of 140 mg/mL AMG 145 in [CCI] mM proline, [C] mM acetate, [CCI] % (w/v) polysorbate 80, pH [CC].

The Personal Injector with prefilled cartridge assembly is a single-use, disposable, on-body electro-mechanical injection device that is co-packaged with a prefilled Crystal Zenith (CZ) cartridge assembly containing 3.5 mL deliverable volume of 120 mg/mL AMG 145 in [CCI] mM proline, [CC] mM acetate, [CCI] % (w/v) polysorbate 80, pH [CC].

AMG 145 should be stored refrigerated and protected from light according to the storage and expiration information provided on the label (where required). AMG 145 should be handled per the instructions provided in the IPIM and the Instructions for Use (IFU) for the prefilled AI/Pen or Personal Injector.

The prefilled AI/Pen or personal injector should be inspected for IP quality, expiry, and damage before using. Damaged, expired, or degraded product should not be used and any issues with the prefilled AI/Pen or personal injector should be reported to Amgen. Further details are provided in the IPIM and IFU.

The lot number of IP is to be recorded on each subject's Drug Administration eCRF.

6.1.1 Dosage, Administration, and Schedule

All investigational product (IP) will be administered at the investigator site by a qualified staff member during site visits or at home or other location by subjects (or designee, which may include a qualified health care professional) between on-site visits. The date, time, and volume of AMG 145 will be collected and recorded on the individual subject's eCRF for doses administered at the study site. IP administration by SC injection at each on-site visit must be done after vital signs, ECG, and blood draw procedures, if applicable.

IP will be administered either at 6 mL via vials and syringes or, depending on device availability at sites; at 3ml via 3 prefilled autoinjectors/pens or at 3.5 ml via 1 personal injector. The 6 mL dose can be split (eg, 3 injections at 2 mL each) and administered into different injection sites. The SC injections should be administered in a consecutive

fashion with all injections completed within 30 minutes. For further details regarding the injection procedures, the IPIM should be consulted.

Parent Study 20110233 Subjects:

Subjects coming from parent study 20110233 will initiate this study with 420 mg SC monthly (QM) dosing. After 12 weeks of 420 mg SC QM, if observed LDL-C reduction is > 5% and PCSK9 levels have been shown to be maximally suppressed (ie, < 100 ng/mL), subjects may continue QM dosing for the duration of the study. In subjects with PCSK9 levels > 100 ng/mL assessed at the end of a 420 mg SC QM dosing interval (eg, assessed at weeks 4 and/or 8), dosing may be changed to 420 mg SC Q2W at the week 12 visit. If the observed LDL-C reduction from baseline is < 5% and PCSK9 levels have been shown to be maximally suppressed (ie, < 100 ng/mL) the subject may be withdrawn from the study at week 12. Depending on the subject response to 420 mg SC Q2W dosing, these subjects may continue Q2W dosing, return to QM dosing, or be withdrawn from the study at the week 24 visit.

Apheresis Subjects:

Subjects on apheresis should initiate treatment with 420 mg SC Q2W in this study to correspond with their apheresis schedule. For apheresis subjects initiating this study on 420 mg Q2W dosing, the dosing schedule may be continued or downtitrated to 420 mg QM at the week 12 visit provided there is evidence of sufficient efficacy (LDL-C reduction of > 5% is considered sufficient efficacy for these subjects). Subjects downtitrating to 420 mg QM dosing at week 12 may revert to 420 mg Q2W dosing 12 weeks after the initiation of 420 mg QM or dosing (eg, week 24) if clinically indicated. Dosing changes that do not occur on week 12 or 24 are permitted in cases where apheresis therapy is discontinued by patients. Dose adjustments after week 24 are discouraged.

Other Subjects:

Subjects that are not receiving apheresis will be provided with AMG 145 420 mg SC QM. Similar to subjects coming from Study 20110233, an option of 420 mg SC Q2W will also be available to other subjects pending observed LDL-C levels and insufficient suppression of PCSK9 (> 100 ng/mL) at the end of a dosing interval (eg, assessed at week 4, 8, etc). Dosing changes should occur at week 12 or 24 if clinically indicated. Dosing changes after week 24 are discouraged.

[figure not shown]
Any other dosing changes must be discussed with the medical monitor. Finally, subjects who have known insufficient efficacy (recommended to be considered as LDL-C reduction < 5% after an adequate trial of AMG 145 dosing) may be removed at either the

week 12 or 24 study visit pending a final risk/benefit discussion with Amgen's medical monitor.

Support for Q2W Dosing with 420 mg:

In a repeat dose (QW, SC) 6 month toxicology study conducted in the cynomolgus monkey, no evidence of toxicity was observed up to the highest dose tested, 300 mg/kg. Based on AUC, this dose level provides a 156-fold exposure margin relative to a 420 mg Q2W clinical dose, respectively.

Study 20080397 also included testing of single dose AMG 145 420 mg IV. Based on the almost 2-fold greater exposure for IV dosing (compared to SC), we anticipate that the C_{max} and AUC over the dosing interval at steady-state to be similar between the two dosing regimens (shown in the left panel of the figure below).

In addition, AMG 145 concentrations are not predicted to exceed the current projection at steady-state over an extended period of 420 mg Q2W dosing (right panel).

The 420 mg dose was selected because of the LDL-C response to this dose observed in other studies, as well as the resulting PCSK9 levels. Additionally, pharmacologic LDL-C reduction in severe familial hypercholesterolemia is known to be extraordinarily difficult to manage due in large part to the fundamental biology underlying the illness, and

current data suggests that subjects with homozygous familial hypercholesterolemia will require more frequent dosing to adequately suppress PCSK9 levels. Thus it is likely that daily doses of AMG 145 greater than those previously administered will provide a substantive therapeutic benefit in this patient population. Details of preparing and administering AMG 145 are included in the IPIM provided by Amgen prior to the start of the study.

After IP administration at each dosing site visit, subjects should be kept for observation for at least 30 minutes before being discharged. The effects of overdose of AMG 145 are not known. All overdose occurrences must be documented, and corresponding AEs recorded on the appropriate eCRF page and in source documents.

Self-administration, defined as SC administration of AMG 145 by the subject, designee or a qualified health care professional will be permitted in a non-site setting (eg, at home or at a location where a qualified health care professional is available). Prior to week 24, subjects that are treated with AMG 145 420 mg administered SC Q2W may self-administer study drug between visits. Starting at the week 24 visit, all subjects will have the option of AMG 145 self-administration. The subject (or designee, if not a qualified healthcare professional) must have demonstrated competency at administration of SC injections before self-administration is permitted: the first self-administered dose by the subject (or designee, if not a healthcare professional) must be administered at the site under the supervision of a healthcare provider. For subjects that prefer not to self-administer AMG 145 or for subjects that will receive AMG 145 during lipid apheresis, AMG 145 may be administered at the site. The dosing schedule is described by a [schema](#) in the protocol synopsis.

6.1.2 Dosage Adjustments

As stated in [Section 6.1.1](#) above, doses may be either uptitrated or downtitrated depending on the starting dose on Day 1. If an investigator wants to make a dose adjustment they must contact the medical monitor and obtain approval prior to doing so. All dose adjustments must be clearly documented and recorded on the appropriate eCRF page and in source documents.

Subjects who are Late for a Scheduled Dose of Investigational Product

Doses Except the Last Dose

Administration of IP should occur within the visit window for each scheduled visit. IP should not be administered within less than 7 days of a previous dose. If a subject arrives for a visit outside the above IP window the dose should not be administered, but all other study procedures should be conducted. These subjects will receive their next SC IP administration as previously scheduled.

Last Dose

Subjects who are late in receiving the last dose of IP at the visit prior to their EOS visit, should receive the dose as soon as possible, regardless of the relationship to visit window. If the last dose has not been received by the EOS visit, it should be omitted entirely.

Subjects who Miss a Scheduled Dose of Investigational Product Completely

Doses Except the Last Dose

Subjects who completely miss a scheduled visit or IP administration will continue in the study and receive scheduled study drug at the next scheduled visit. If a dose is missed between quarterly visits, the dose should not be administered within 7 days of the previous dose or within 7 days of the next scheduled dose.

Last Dose

Subjects who completely miss the last scheduled IP administration will continue in the study and should return for an unscheduled visit as soon as possible to receive study drug. If the last dose has not been received by the EOS visit, it should be omitted entirely.

6.1.3 Criteria for Withholding of Investigational Product

Reports from the central laboratory after each visit must be reviewed as soon as possible after receipt and before the next administration of IP. If any of the criteria below are met for withholding IP, statin, or other applicable background lipid therapy, the subject must be instructed to stop the applicable treatment and an additional visit must be scheduled for the required laboratory evaluations. If a subject is experiencing elevations of laboratory values below (Sections 6.1.3.1 and 6.1.3.2) and is receiving other lipid therapies that may result in such elevations, eg, ezetimibe, fenofibrate, or niacin, the additional therapies should also be evaluated for a potential role in these

elevations and considered for discontinuation. Fenofibrate, ezetimibe, or niacin can result in elevation of CK or liver function tests. If a subject experiences elevations in triglycerides > 500 mg/dL (5.65 mmol/L) and is concomitantly receiving a bile acid binding resin, the bile acid binding resin should be evaluated for discontinuation.

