7.1.3.3 Lipid Measurements

Investigators and staff involved with this trial should remain blinded to locally obtained lipid panels until the week 8 visit for all subjects that transition from an ongoing blinded (or blinded portion) parent study into this study, in order to avoid potential unblinding of the ongoing parent study.

If a lipid panel is drawn during the first 8 weeks, all reasonable steps must be undertaken to avoid informing the subject and study personnel of the results.

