7.1.3.4 Laboratory Assessments

All on-study laboratory samples will be processed and sent to the central laboratory. Amgen or designee will be responsible for PK (AMG 145 and PCSK9 serum levels), anti-AMG 145 antibody, and biomarker development assessments and the central laboratory will ship the samples to Amgen or a specialty laboratory for assay (depending on the assessment).

The central laboratory will provide a study manual that outlines handling, labeling, and shipping procedures for all blood samples. The date and time of sample collection will be recorded in the source documents at the site.

[Table 3](#) below outlines the specific analytes for serum chemistry, hematology, urinalysis, and other testing to be conducted.

Table 3. Analyte Listing

Chemistry	Coagulation	Urinalysis	Hematology	Other Labs
Sodium	PT/INR	Specific gravity	Hemoglobin	Fasting lipids
Potassium		pH	Hematocrit	• Total cholesterol
Chloride		Blood	MCV	• HDL-C
Bicarbonate		Protein	MCH	• LDL-C
Total protein		Glucose	MCHC	• Triglycerides
Albumin		Bilirubin	RDW	• VLDL
Calcium		WBC	Platelets	• Non-HDL-C
Magnesium		RBC	RBC	ApoA1
Phosphorus		Epithelial cells	WBC	ApoB
Glucose		Bacteria	Differential	ApoB/ApoA1 ratio
BUN or Urea		Casts	• Neutrophils	Total Cholesterol/HDL-C
Creatinine		Crystals	• Bands	hsCRP
Uric acid			• Eosinophils	Lp(a)
Total bilirubin			• Basophils	Anti-AMG 145 antibodies
Direct bilirubin			• Lymphocytes	AMG 145 (PK)
CK			• Monocytes	PCSK9
ALP				HbA1c
LDH				FSH
AST (SGOT)				Fasting Vitamin E
ALT (SGPT)				eGFR (calculated)
				Serum HcG

Central laboratory results of the lipid panel, ApoA1, ApoB, Lp(a), and hsCRP will not be reported to the investigator prior to week 8 for subjects coming from a blinded (or blinded portion) of a parent study, since some laboratory results may inadvertently unblind investigators to treatment assignment in the parent study. Subjects coming from a blinded (or blinded portion) parent study will have AMG 145 and PCSK9 levels blinded until week 4 since some laboratory results may inadvertently unblind investigators to treatment assignment in the parent study. Vitamin E samples will be blinded to investigators and subjects in the first 96 weeks of the study. Investigators should not perform local testing of these analytes during this time.

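### Until week 8, investigators cannot see the triglyceride value needed for the Section 6.1.3 bile acid resin check in rollovers from a blinded parent study whose results are not yet public

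*Protocol*

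**What the plan says.** Section 6.1.3 of the protocol makes central laboratory reports the basis for its checks: "Reports from the central laboratory after each visit must be reviewed as soon as possible after receipt and before the next administration of IP". Its triglyceride provision begins "If a subject experiences elevations in triglycerides > 500 mg/dL (5.65 mmol/L) and is concomitantly receiving a bile acid binding resin" and concludes that "the bile acid binding resin should be evaluated for discontinuation". This is advice about a background drug, not a criterion for withholding AMG 145.

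Table 3 in Section 7.1.3.4 lists triglycerides under fasting lipids. The same section says "Central laboratory results of the lipid panel, ApoA1, ApoB, Lp(a), and hsCRP will not be reported to the investigator prior to week 8" for subjects who come from a blinded parent study or the blinded portion of one. It adds: "Investigators should not perform local testing of these analytes during this time".

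Section 7.1.3.3 covers locally obtained panels. Staff stay blinded to them until the week 8 visit "for all subjects that transition from an ongoing blinded (or blinded portion) parent study into this study". If a panel is drawn in that time, "all reasonable steps must be undertaken to avoid informing the subject and study personnel of the results".

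Section 3.1 (and SAP Section 3.1) attaches a further limit to the masking, which on one reading ends it once the parent study's results are public. The synopsis and Section 7.1.3.4 do not repeat that limit.

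**The concern.** The person asked to act on a triglyceride value is the person from whom it is withheld. The samples are taken and the central laboratory holds the results, but for these rollovers the plan gives no way for a value above 500 mg/dL to reach the site before week 8.

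Two features of the plan add to this. The triglyceride entry limit of 400 mg/dL in 4.1.5 applies only to subjects who did not come from a parent study, so this study sets no such limit for rollovers. Section 6.3 also asks that lipid-regulating drugs be left alone before week 12 unless there is a clinically compelling reason to change them. A resin would therefore normally continue, and the result that might justify stopping it is hidden for most of that period.

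What is at stake is a delay in an advisory safety check, not the validity of any analysis.

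**Working it through.** The plan gives no figure on this point to reproduce. The check compares the relevant sections and then counts.

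**Is triglyceride part of the masked panel?** The protocol does not formally define the term lipid panel. Table 3 puts triglycerides among the fasting lipids, and the footnote to SAP Table A.2 uses lipid panel for the fasting plasma lipids, leaving out only direct VLDL and direct LDL. No text releases triglycerides separately. The threshold is coherent across sections: 500 mg/dL is given as 5.65 mmol/L, so 400 mg/dL is 400 × 5.65/500 = 4.52 mmol/L, matching the 4.5 in 4.1.5.

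**Is there another route to the value?**

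| Route | Section | What it provides |
|---|---|---|
| Central laboratory report | 7.1.3.4 | Withheld until week 8 |
| Local test | 7.1.3.4, 7.1.3.3 | Should not be done; if done, result kept from staff |
| Retest at screening | 7.1.1.1 | Triglycerides may be retested, but the lipid panel may need to be avoided in subjects from a blinded parent study; screening only |
| Extra tests on collected blood | 7.1.3.2 | Allowed for subject safety; silent on releasing masked results |
| Medical monitor | 6.3 | Available for a compelling clinical reason, but does not supply the value |

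The creatine kinase and liver rules (6.1.3.1, 6.1.3.2) do not share the problem, because chemistry is not masked.

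**Scheduled lipid panels for a direct rollover (Appendix A, Section 7.1.2)**

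- Day 1: 1
- Weeks 4, 6, 8, 16 and 20: 5
- Quarterly, weeks 12 to 252: 252/12 = 21
- Week 260: 1
- Total: 1 + 5 + 21 + 1 = 28

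The masked panels are Day 1, week 4 and week 6: 3/28 = 10.7%. A rollover who missed the 1-month window has one screening panel more: up to 4/29 = 13.8%. In time, 8/260 weeks = 3.1%.

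**Before week 12.** The panels are Day 1 and weeks 4, 6 and 8. Three of these four (75%) are masked, covering 8/12 = 67% of the period in which Section 6.3 discourages changes to lipid drugs.

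**Subjects.** Study 20110233 has a planned size of 59 (Section 2.2.4): 59/310 = 19.0%. This is a ceiling, since SAP Section 9.4 names only Part B of that study. The number from other blinded parent studies is not given, nor is the number on a resin with triglycerides above 500 mg/dL.

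**Would a flag unblind the parent study?** In Table 2, at 420 mg Q4W, the difference from placebo is -9.14% for triglycerides (95% CI -19.64 to 1.37), against -55.99% for LDL-C. Over the six regimens the triglyceride differences run from -7.28% to -25.27%. A flag on triglycerides alone therefore says little about allocation. Of the three masked panels in a direct rollover, only Day 1 is drawn before every rollover receives AMG 145 in this study.

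**The case against.** The strongest reply is that nothing is breached. Section 6.1.3 requires review after receipt, so a report that is not issued creates no duty, and the resin step is only advisory. Masking the lipid panel is a deliberate choice to protect the parent blind. This stands: it is a gap and not a contradiction.

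Second, an alert may exist outside these documents. The protocol says of the laboratory manual: "The central laboratory will provide a study manual that outlines handling, labeling, and shipping procedures for all blood samples". That description does not mention alerts but does not exclude one. The Amendment 5 rationale also says the sponsor continues safety monitoring. The possibility of a manual alert stands. The monitoring remark gives no route by which a masked value would reach the site.

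Third, the Day 1 panel doubles as the parent study's final visit, so access to it may be governed by the parent protocol. Without it the count is 2/27 = 7.4%. Appendix A schedules the Day 1 panel in this study, so 3/28 is kept; the conclusion is the same either way.

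Fourth, the affected group may be very small or even empty by the SAP date. SAP Section 10.1 says the interim analysis had already summarized subjects by assigned 20110233 treatment. The documents do not say when parent results became public, so this cannot be settled. Section 4 lets subjects from future qualifying studies enter if the sponsor agrees, so the situation could recur.

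Finally, no added risk is shown. Any parent-study triglyceride limit is not given, and triglyceride point estimates fall in all six Table 2 regimens, so new rises on AMG 145 are not specially expected. This also stands, and it keeps the point minor.

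**Conclusion.** The concern holds, as a minor point. Followed as written, the plan leaves the resin check unusable on scheduled results until week 8 for rollovers from a blinded parent study whose results are not yet public. The practical effect is an 8-week delay in an advisory check, for a fraction of at most 19% of subjects from study 20110233 plus an unstated number from other blinded parent studies. A symptomatic subject can still be taken to the medical monitor.

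This rests on three assumptions: that lipid panel includes triglycerides, that the laboratory manual holds no alert, and that few subjects take a resin and exceed 500 mg/dL. The first is well supported by the text; the other two cannot be checked from the documents.

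**What to change.** Add one sentence to Sections 6.1.3 and 7.1.3.4: during the masked period, the central laboratory or the medical monitor notifies the site only that a triglyceride value exceeds 500 mg/dL, while the rest of the lipid panel, ApoA1, ApoB, Lp(a) and hsCRP stay masked. If the laboratory manual already provides this, cite it there instead. The public-results clause in Section 3.1 can stay as it is.

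The cost is a sentence and a laboratory alert setting. The drawback is an unblinding risk that looks very small on the Table 2 figures, with two cautions: Table 2 pools four studies, none in homozygous FH, whereas 20110233 is a homozygous FH study; and the parent-study regimen is not given, so using the 420 mg Q4W row is an assumption.
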